16.6 Follow-up of Adverse Events

All AEs (both serious and non-serious) should be followed until resolution or until a stable clinical endpoint is reached. All measures required for AE management and the ultimate outcome of the AE must be recorded in the source document and reported to the Sponsor.

17.0 EXTERNAL DATA SAFETY MONITORING BOARD

An External Data Safety Monitoring Board (DSMB) will continuously evaluate toxicity and mortality rates, and recommend appropriate actions, according to the DSMB Charter.

18.0 STATISTICAL METHODS

18.1 Overview of Analysis

18.1.1 Safety Parameters

- Adverse events related to the surgical procedure
- SB623-related adverse events
- Adverse changes imaged by head MRI (edema, adverse anatomical changes)
- Serious adverse events (SAEs)
- Serum chemistry and hematology

18.1.2 Efficacy Parameters

- Clinical improvement of stroke symptoms using the European Stroke Scale, the NIH Stroke Scale, and the Modified Rankin Scale; improvement in motor functions using the Fugl-Meyer scale, and improvement in cognitive status using a test battery (including Rey Complex Figure Test; see Appendix D)
- Increase in fluorodeoxyglucose (FDG) uptake measured by PET

18.1.3 Efficacy Objectives

Primary:

• To evaluate clinical (ESS) and radiographic (FDG-PET) response to 3 dose levels of intracranial administration of SB623 cells at 6 months

Secondary:

- To evaluate clinical (NIHSS, MRS, Fugl-Meyer, Cognitive Tests) response to 3 dose levels of intracranial administration of SB623 cells at 6 months
- To evaluate clinical (ESS, NIHSS), MRS, and Fugl-Meyer response to 3 dose levels of intracranial administration of SB623 cells at 1, 2, 3, 4, 9, 12, and 24 months; also to evaluate changes from Baseline in cognitive function at 6, 12, and 24 mos., and changes from Baseline in radiographic (DFG-PET) responses at 6, 12, and 24 mos.

18.2 Patients to be Included in the Analyses

18.2.1 Efficacy Population

The intent-to-treat (ITT) population will include all enrolled patients, including those who were discontinued from the study or withdrawn for any reason. The Evaluable population will be defined in the Statistical Analysis Plan.

18.2.2 Safety Population

The safety analyses will include all enrolled patients who have received Study Drug and who have any post-Baseline data.

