7.0 SURGICAL AND IMPLANTATION PROCEDURES

The surgical procedure is a modification of one used earlier with another cell product,^{29,54} and which has been shown to have a high degree of safety in a retrospective study of over 2,600 patients undergoing stereotactic surgery over the course of 28 years at one major clinic.³⁰ On the morning of surgery, a standard stereotactic coordinate frame (Leksell Stereotactic System®, manufactured by Elekta⁵⁵) is to be applied to the head under local anesthesia and mild sedation. Either a head CT scan overlaid on the Baseline MRI or a head MRI scan alone is to be performed for stereotactic targeting. The MRI scans are to use insulated posts an RIF transmitter head, and 1.5 tesla. A safe trajectory is to be defined to enter a cortical gyrus, sparing a sulcus. Points are to be determined in the basal ganglia inferior to the stroke and beyond the stroke. Three needle tracks are to be determined with trajectories in the same paramedian plane spaced by 5-6 mm at the target

One burr-hole craniostomy (1-1.5 cm) is to be fashioned under local anesthesia. The dura is to be opened and a 1.8-mm outer-diameter. 15-cm long stabilizing cannula containing a removable solid stylet is to be inserted to a point just proximal to the penumbra of the stroke area. The solid stylet is then to be removed, followed by insertion into the stabilizing cannula of a 0.9-mm outer diameter, 19-cm. long, 20-µL volume Pittsburgh Implantation Cannula (previously qualified for product stability and delivery and provided by the Sponsor) down to the deepest target point for the first implantation. A total volume of 100 μ L of cell suspension is to be aspirated into a 100- μ L syringe through the implant cannula. The implantation cannula is then to be filled with cell suspension. Five 20-µL volumes of cells are to be injected slowly (approximately 10 μ L/min.) into 5 implantation sites, slowly withdrawing the stabilizing needle probe so that the implantations are spaced as equally as possible (intervals of 4-5 mm) with 2-3 implants within the penumbra distal to the stroke area and 2-3 implants within the penumbra proximal to the stroke area. The target locations will be selected by the site neurosurgeon and neurologist to be closest to the motor pathway based on the patient's own neuroanatomy. This procedure is to be repeated with 2 other needle tracks with different trajectories, inserted through the same burr-hole craniostomy.

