10.3.2 Enrollment (Days -1 or 1)

Enrollment can only occur after performing all assessments and verifying that the patient meets the inclusion and exclusion criteria for the study.

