11.4 Preparation and Administration

Details for preparation of the cell suspension for administration will be provided by the Sponsor. Clinical sites will be provided necessary materials for reconstitution of the cells and will be trained by the Sponsor. The cryopreserved cells will be thawed, washed, centrifuged, and re-suspended in Plasma-Lyte A at varying concentrations (see Section 4.1) for administration to the patient within approximately 3 hours of re-suspension. Prior to administration, a gram stain and a test for endotoxin will be done and a sterility test initiated on the last cell wash to insure continued sterility. If the endotoxin level is > 5 EU/mL or the gram stain is positive, implantation will not occur. If the sterility test is positive, an investigation will be conducted to determine the source of the contamination. In addition, identification of the pathogen and sensitivity will be done and the patient treated with an appropriate antibiotic. In this event, the patient will be followed closely for adverse events associated with a possible infection and response to antimicrobial therapy, including frequent clinic visits until any infection is cleared.

This Investigational Product may not be used for any purpose other than this clinical study.

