4. ANALYSIS SETS

4.1 EFFICACY POPULATION

Intent-to-Treat (ITT): The intent-to-treat (ITT) population will include all enrolled patients. Enrolled patients are patients who meet all inclusion/exclusion criteria and qualified for the study or who were granted exceptions to selected inclusion/exclusion criteria, meet all other inclusion/exclusion criteria and qualified for the study, including those who were discontinued from the study or withdrawn for any reason. The ITT population will be used in all efficacy analyses.

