4.2 SAFETY POPULATION

Safety Population: The safety population will include all enrolled patients who have received treatment with SB623 and who have any post-baseline data. The safety population will be used in all safety analyses.

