6.2 SAFETY ENDPOINTS

The safety and tolerability of SB623 cells will be summarized in terms of the following:

- Adverse events (AEs)
- Dose-Limiting Toxicities (DLTs) grade 3 or higher events related to study product or administration procedure
- AEs related to the surgical procedure
- SB623-related AEs
- Serious Adverse Events (SAEs)
- Adverse changes imaged by head magnetic resonance imaging (MRI) (edema, adverse anatomical changes)
- Clinically significant changes in laboratory tests
- Clinically significant changes in physical exam and vital signs
- Development of SB623 serum antibodies
- Changes in PBMC function
- Changes in plasma cytokines

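### The safety set requires receipt of SB623, so a patient whose operation is started but abandoned before any deposit is in none of the adverse-event tables

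*Protocol*

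**What the plan says.** Both documents make receipt of cells a condition of the safety set. Protocol 18.2.2: "The safety analyses will include all enrolled patients who have received Study Drug and who have any post-Baseline data". SAP 4.2: "The safety population will include all enrolled patients who have received treatment with SB623 and who have any post-baseline data". SAP 4.2 applies that set to every safety analysis, and SAP 9.2 marks all five adverse-event tables (14.3.1.1-14.3.1.5) as Safety.

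Enrollment falls on Day -1 or 1 and depends on eligibility, not dosing: "Enrollment can only occur after performing all assessments and verifying that the patient meets the inclusion and exclusion criteria for the study" (Protocol 10.3.2). The efficacy set follows enrollment: "The intent-to-treat (ITT) population will include all enrolled patients" (SAP 4.1).

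Protocol 7.0 gives the order of the operation. The head frame goes on first and targeting imaging follows. Then "One burr-hole craniostomy (1-1.5 cm) is to be fashioned under local anesthesia". The dura is opened and the cannulas are inserted before any cells are injected.

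Surgical events are a safety endpoint in their own right, listed apart from SB623-related events: "Adverse events related to the surgical procedure" (Protocol 18.1.1) and "AEs related to the surgical procedure" (SAP 6.2).

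The protocol also foresees not implanting for a product reason: "If the endotoxin level is > 5 EU/mL or the gram stain is positive, implantation will not occur" (11.4). It does not say whether these results must be available before surgery begins.

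**The concern.** The primary objective is the safety of intracranial administration, and part of that risk arises before any cells are given. A safety set of treated patients works well when risk begins with the product. Here, membership can be decided by what happens during the operation. If a bleed or seizure ends surgery before the first deposit, the patient leaves both the numerator and the denominator of the rate that the event should inform. With about 18 patients, tabulated by cohort of 6 as well as pooled, one missing case visibly changes the reported rate.

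**Working it through.** **1. Membership check.** Take an enrolled patient with a burr hole and cannula in place and no deposit.
- ITT (SAP 4.1): yes, because the patient is enrolled.
- Safety (Protocol 18.2.2, SAP 4.2): no, because no SB623 was received.
- Adverse-event tables that include the patient: 0 of 5. No adverse-event table uses ITT or All Patients.

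A patient whose event occurs at or after the first of the 15 deposits (3 tracks x 5) has received SB623 and meets that condition. The gap concerns zero-deposit patients only.

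**2. The plan's own figure.** Protocol 18.5 states a chance below 5% of missing a dose-limiting toxicity with 6 patients at a true rate of 40%. This reproduces: 0.6^6 = 0.0467. It does not depend on the safety-set definition. The documents give no rate of aborted operations and no replacement rule, so what follows is illustration.

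**3. Effect of one case.** Assume one pre-deposit event that ends the operation and no such event in the implanted patients. Exact (Clopper-Pearson) 95% limits are the 0.025 quantile of Beta(x, n-x+1) and the 0.975 quantile of Beta(x+1, n-x), with the lower limit 0 when x = 0.

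| Setting | Current set | Procedure-started set |
|---|---|---|
| 18 others implanted | 0/18 = 0% (0-18.5%) | 1/19 = 5.3% (0.1-26.0%) |
| Aborted case not replaced | 0/17 = 0% (0-19.5%) | 1/18 = 5.6% (0.1-27.3%) |
| One cohort, 6 implanted | 0/6 = 0% (0-45.9%) | 1/7 = 14.3% (0.4-57.9%) |

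**4. How likely it is.** Protocol 2.2.4 quotes hematoma evacuation by craniotomy at 0.36% and perioperative seizure at 0.36%; the sum is 0.72%. Let s be the share that both occurs before the first deposit and ends the operation. The documents do not give s; 5-25% is assumed. With r = 0.0072 x s, P(at least one in 18) = 1 - (1 - r)^18:
- s = 5%: r = 0.00036, P = 0.6%
- s = 25%: r = 0.0018, P = 3.2%
- s = 100%: r = 0.0072, P = 12.2%

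**5. A separate inconsistency: a pre-deposit event in a patient who is then implanted.**
- Pointing to exclusion: the adverse-event and SAE windows open at dosing (Protocol 16.2, 16.5; SAP 7.4.1), and SAP 7.2.6 assigns changes between consent and treatment administration to medical history.
- Pointing to capture: Table 4 marks adverse events, and leaves medical history blank, in the cell-administration column. SAP 7.4.2 has post-baseline MRI changes reported as adverse events. SAP 7.2.4 describes the burr hole under treatment exposure.

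On the strict reading, an event that did not later worsen could be left out of the treatment-emergent tables (14.3.1.1-14.3.1.3). The discontinuation and SAE tables (14.3.1.4-14.3.1.5) are not limited to treatment-emergent events but depend on what the window admits.

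**The case against.** A treated-patients safety set is a recognised choice, and both documents apply it consistently. The scenario is remote, the 5-25% share has no source, and the intervals in the table overlap almost entirely. No test is run on adverse-event rates, and in a study this small an aborted operation would be read as an individual case. It would not be hidden. Protocol 14.0 sends surgical events to the DSMB, and 16.1 puts procedural complications under expedited reporting. The disposition tables cover All Patients, the listings state no population, and SAP 7.4.1 lists all adverse events. Protocol 13.3 with 10.10 provides an early-withdrawal visit that includes adverse events, head MRI and stroke evaluations.

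Most of this stands, and it limits the point. It does not answer it: those routes give oversight and individual records, whereas the tabulated incidence would still omit the case.

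Two stronger readings are tempting and fail. A reader might infer that the set generally removes the patient with the worst surgical outcome. It does not, because bleeding, seizure or death at or after the first deposit does not undo receipt of SB623. A reader might also count a failed endotoxin or gram-stain test as a further source of lost safety events. The documents do not show that such a patient would have been operated on, or would have had any adverse event.

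**Conclusion.** The point holds for enrolled patients whose operation is started and abandoned with no deposit. They are in ITT and in none of Tables 14.3.1.1-14.3.1.5, although surgical adverse events are a named endpoint. The membership result follows from the wording alone. The likelihood of 0.6-3.2% rests on the assumed share and on two complication rates from a general stereotactic series. The 12.2% is an upper value for those two complications only, not for aborted operations in general. The change from 0/18 to 1/19, or from 0/6 to 1/7, assumes one such case.

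For implanted patients with a pre-deposit event, a reader might infer outright exclusion. The documents conflict instead, and the passages must be reconciled. The rule that stops dosing at 2 of 6 is not affected, because it counts toxicities attributed to the cells. The change is worth making before any such case arises; redefining the set afterwards would be a post-hoc decision.

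**What to change.** Define the safety population as all enrolled patients in whom the Day 1 surgical procedure is started, whether or not cells are implanted. State the start point once; frame application is the first surgical step in 7.0, but another step may be chosen. Use it for adverse-event and SAE collection, the treatment-emergent reference and the end of the medical-history period. The sections to align are Protocol 10.4, 16.1, 16.2, 16.5, 18.2.2 and 18.4, and SAP 4.2, 7.2.6, 7.4 and 7.4.1. This also settles the conflict for implanted patients.

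Let Table 5 record relationship to the procedure as well as to Study Drug. Tabulate surgical-procedure events on the procedure-started set (SAP 9.2 currently lists no such table) and SB623-related events on the implanted subset. For a non-implanted patient, use the existing early-withdrawal visit (13.3, 10.10). Count any further adverse-event follow-up from the procedure date, because the current windows run from SB623 administration and the follow-up in 13.3 is counted from implantation.

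The cost is two denominators if an operation is aborted, one added summary, and a small addition to adverse-event data collection.

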18.3 Analysis of Efficacy

18.3.1 Primary Analysis

The primary analysis will be a pooled analysis of changes at 6 months from Baseline for all patients for ESS and FDG-PET parameters. Categorical variables will be summarized by frequency and percent. Continuous variable data will be summarized, including mean, median, standard deviation and range. Statistics will be done on changes in scores, and will be based on Wilcoxon Signed Rank test unless otherwise specified in the Statistical Analysis Plan.

18.3.2 Secondary Analyses

The secondary analyses will be pooled analyses of changes from Baseline at 1, 2, 3, 4, 6, 9, 12, and 24 months for all patients for ESS, NIHSS, MRS, and Fugl-Meyer. Evaluation of changes from Baseline for Cognitive Tests, and FDG-PET parameters will be done at months 6, 12, and 24. In addition, possible dose-response will be determined. Statistics will be done as for the Primary Analysis.

18.4 Analysis of Safety

Adverse events, clinical laboratory data, and vital signs will be analyzed to evaluate the safety of SB623 for all patients in the Safety population through 2 years after the dose of Study Drug.

A treatment-emergent adverse event will be defined as any event not present prior to the initiation of treatment or any event already present that worsens in either intensity or frequency following exposure to study treatment.

All adverse event data will be listed per patient including severity, relationship to Study Drug, and action taken. Frequency within each treatment group of each type of adverse event will be summarized using an acceptable coding dictionary.

Laboratory data and vital signs will be listed by patient. Laboratory data values above and below normal ranges which are considered clinically significant will be indicated on the listing. Descriptive statistics will be displayed for each laboratory parameter and vital sign assessment at each time point. The mean change from baseline in each of these continuous variables will also be described.

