6.2 Objectives

6.2.1 Primary Objective

The primary objective is to determine acute and long-term safety of SB623 cells administered stereotactically around the infarct region of brains of patients with stable ischemic stroke.

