16.2 Adverse Event Reporting Period

The adverse event reporting period for this trial begins upon receiving the first dose of Study Drug and ends 24 weeks after the administration of SB623.

All AEs (both serious and non-serious) must be followed until resolution or until a stable clinical endpoint is reached. All measures required for AE management and the ultimate outcome of the AE must be recorded in the source document and reported to the Sponsor.

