16.5 Reporting Serious or Unexpected AEs

Any Serious Adverse Event, including death that occurs during this study (from the first dose of Study Drug up to and including 4 weeks following the last dose of Study Drug), whether or not the event is considered to be related to the study treatment, must be reported immediately (within 24 hours after the site becomes aware of the event) to the Principal Monitor.

The contact information for reporting SAEs is as follows:

[name]. [contact] ext 44 [contact] Email: [contact] The Investigator is encouraged to discuss with the Principal Monitor any adverse experiences for which the issue of reportability is unclear or questioned.

A verbal or faxed Serious Adverse Event Report must be followed by a written report signed by the Investigator within 48 hours. Written notification must include SAE start and stop dates, Study Drug dosage and treatment history, description of SAE with applicable laboratory test results, list of concomitant medications, relationship of Study Drug to SAE, autopsy report (if applicable), and any other relevant information such as medical history, hospital discharge summary, *etc.* The report should be as complete as possible without delaying Sponsor notification.

An SAE Report should be prepared containing as much available information concerning the event as possible so that a written report can be filed with the appropriate regulatory authorities. Any SAE follow-up information requested by the Sponsor or the Sponsor's designee should be provided in a timely manner.

Upon receipt of notification of any Serious Adverse Event, the Sponsor will immediately conduct an evaluation of the event and take action indicated by the results of the evaluation. This may include notification of the FDA, other Investigators, IRBs and/or the suspension or termination of the study. The Investigator is required to report Serious Adverse Events and Unexpected Adverse Events to the local Ethics Committee (EC) or Institutional Review Board (IRB) in accordance with the EC/IRB bylaws.

All additional follow-up evaluations of the SAE must be reported to the Sponsor. These data should be faxed to the Principal Monitor at [contact] as soon as they are available.

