7.4.1 Adverse Events

A treatment-emergent adverse event (TEAE) is defined as any event not present prior to study treatment administration or any event already present that worsens in either intensity or frequency following exposure to study treatment.

Adverse events will be classified based on the Medical Dictionary for Regulatory Activities (MedDRA) dictionary, version 15.1 (or higher). Analyses will be conducted on preferred term and primary system organ class (SOC). All adverse event data will be listed per patient including severity, relationship to study treatment, and action taken. Event severity is based on the World Health Organization (WHO) standard toxicity criteria (STC).

A Dose-limiting toxicity (DLT) will be defined as any grade 3 or 4 event which is at least possibly related to study product or administration procedure.

The adverse event reporting period for this trial begins upon receiving the dose of study treatment and ends 24 months after the administration of SB623.

The following summaries of AEs will be provided:

- TEAEs by MedDRA SOC and by preferred term
- TEAEs by maximum severity (mild, moderate, severe, life-threatening) by MedDRA SOC and preferred term
- TEAEs by relationship to study treatment by not related (includes unrelated and unlikely related) or related (includes possibly, probably, and definitely related) by MedDRA SOC and preferred term.
- AEs resulting in discontinuation from the study, by MedDRA SOC and preferred term
- SAEs by MedDRA SOC and preferred term
- The following listings of adverse events will be provided (TEAEs will be denoted in each listing):
 - o All AEs
 - All Dose-Limiting Toxicities (DLTs)
 - o Adverse events resulting in discontinuation from the study
 - o Deaths (if any)
 - o Serious adverse events
 - AE mappings to MedDRA dictionary terms

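### No planned adverse-event summary table is split by time since implantation, so the tables do not report acute and late harm separately, although both belong to the primary objective

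*Protocol*

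**What the plan says.** Protocol 6.2.1 states: "The primary objective is to determine acute and long-term safety of SB623 cells". Protocol 18.4 analyses safety "through 2 years after the dose of Study Drug" and, for AEs, plans a per-patient listing and one kind of summary: "Frequency within each treatment group of each type of adverse event will be summarized using an acceptable coding dictionary".

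SAP 7.4.1 carries this out with five summaries. The first is "TEAEs by MedDRA SOC and by preferred term". The others are by maximum severity, by relationship to study treatment (related or not related), AEs leading to discontinuation, and serious AEs (SAEs). They appear in SAP 9.2 as Tables 14.3.1.1 to 14.3.1.5. None is defined by visit, study day, period or time to onset.

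SAP 7.5 adds one interim analysis on Month 6 data, once the last patient enrolled has completed that visit. It produces all tables, listings and figures. The SAP addendum deals only with Fugl-Meyer scoring and leaves the AE outputs unchanged.

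The AE reporting period differs between places. SAP 7.4.1 says it "begins upon receiving the dose of study treatment and ends 24 months after the administration of SB623". Protocol 16.2 says it "ends 24 weeks after the administration of SB623".

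**The concern.** Treatment is a single operation followed by two years of observation, with no control arm. Whether an event began in the week of surgery or a year later is one of the few internal clues to its origin. It is also what distinguishes the two parts of the objective in protocol 6.2.1. A count of patients ever affected adds the parts together. A term that is common around surgery can then mask later first occurrences of the same term, and a reader of the tables alone cannot say how much of the total is acute.

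The SAP does use time elsewhere: change from baseline in laboratory values and vital signs is tabulated by visit. AEs, the first safety endpoint in SAP 6.2, are not. AEs related to the surgical procedure are a separate endpoint in protocol 18.1.1 and SAP 6.2, but no table or listing in SAP 9.2 or 9.3 is dedicated to them. Table 14.3.1.3 splits only by relationship to study treatment.

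**Working it through.** **1. The plan's own figure.** Protocol 18.5 gives less than a 5% chance of missing a dose-limiting toxicity (DLT) in a cohort of 6 if the true rate is 40%. Exact binomial: (1 − 0.40)^6 = 0.0467, so it reproduces. The figure has no time window.

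**2. Which outputs carry time?**

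| Output | Split by time? |
|---|---|
| Tables 14.3.1.1 to 14.3.1.5 | No |
| Laboratory and vital-sign change tables | By visit |
| MRI listing (SAP 7.4.2) | By follow-up visit, presence or absence only; details go to the AE data |
| AE, DLT and SAE listings | Per patient; SAP 7.4.1 names severity, relationship and action taken, not onset day |
| Month 6 interim (SAP 7.5) | One cut, covering surgery week to Month 6 |

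**3. What the interim cut can and cannot show.** This is an illustration. Assume that nine of 18 patients have a first headache, with the same grade and relationship in each pattern, and that tables count patients (SAP 7.1). 9/18 = 50%.

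| Onset | Interim | Final |
|---|---|---|
| A: week 1 | 9 (50%) | 9 (50%) |
| B: Day 9 to Month 6 | 9 (50%) | 9 (50%) |
| C: after Month 6 | 0, if AEs are cut at each patient's Month 6 | 9 (50%) |

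A and C differ at the interim if the cut is applied. A and B never differ. If the patients in A also have new headaches after Month 6, the interim and final counts are still 9 and 9, so subtracting one from the other gives 0.

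**4. Whether the interim is a clean cut.** Minimum time from first to last dosing, from the stagger in protocol 9.1:
- Cohort 1: 5 × 2 = 10 weeks.
- Cohorts 2 and 3: 4 + 2 + 2 = 8 weeks each, if patients 4 to 6 may follow patient 3 at once.
- Total: 10 + 8 + 8 = 26 weeks.

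When the last patient reaches Month 6, the first has at least about 12 months of follow-up. The SAP does not say whether that patient's AEs after Month 6 enter the interim tables.

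**5. Reporting period.** 24 weeks = 24 × 7 = 168 days. 24 months = 24 × 30.4375 = 730.5 days. 168/730.5 = 23%, so 77% of the SAP's period falls after reporting ends under protocol 16.2. Month 6 is 6 × 30.4375 = 182.6 days, already beyond day 168, so a window after Month 6 lies wholly outside 16.2. Yet the schedules in protocol Table 4 and SAP 10.1 assess AEs through Month 24. Protocol 16.5 has a shorter window still for immediate SAE reporting: "from the first dose of Study Drug up to and including 4 weeks following the last dose of Study Drug".

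**6. One total, several time patterns.** The documents give no early/late split, so this is an assumed range. It divides a 40% cumulative rate between two windows, independent within a patient: late = 1 − 0.60/(1 − early).

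| Early | Late | No early event in 6 | No late event in 6 |
|---|---|---|---|
| 10% | 33.3% | 0.9^6 = 53.1% | 0.667^6 = 8.8% |
| 20% | 25% | 0.8^6 = 26.2% | 0.75^6 = 17.8% |
| 30% | 14.3% | 0.7^6 = 11.8% | 0.857^6 = 39.7% |

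All three rows have the same expected overall frequency.

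**7. What an empty cell would mean.** With no events, the one-sided 95% upper bound is 1 − 0.05^(1/n): 39.3% for n = 6 and 15.3% for n = 18.

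**The case against.** The strongest reply is that the plan holds more timing information than its AE table titles suggest. All AEs are listed per patient, with separate listings for DLTs, SAEs and deaths; MRI change is listed by visit; and 18 patients can be read line by line. The listing items are introduced as inclusive, so onset day may well appear, and protocol 16.5 requires start and stop dates in SAE reports. The AE tables are run twice, not once. The documents also rely on attribution: the investigator grades relationship, and the data safety monitoring board is the final arbiter. The animal data in protocol 3.4 put cell clearance at around one month in nude rats and monkeys, so early effects of the cells could overlap with surgery and onset windows need not separate those two causes. Finally, the synopsis and SAP 2.1 word the objective simply as safety and tolerability over two years.

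Much of this stands. A reader might infer that acute and late harm cannot be told apart, that opposite patterns must always give identical tables, or that the tables answer neither half of the objective. The documents support none of these: the listings may separate the events, the Month 6 run can distinguish pattern A from pattern C, and an overall frequency is still evidence on safety.

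What remains is narrower. Protocol 6.2.1 names both acute and long-term safety, no AE summary separates them, and the Month 6 run does not isolate the perioperative period. A listing without a named onset day is not a prespecified summary. The general rule in SAP 7.1, to summarise by time point when appropriate, is not carried into the AE tables.

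**Conclusion.** The point holds as a reporting gap in the summary tables, and the label is a cheap improvement. Acute and late AEs are not tabulated separately, and the single Month 6 cut is coarse and not fully defined. No sample-size figure changes, and no bias in an estimate is claimed.

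The headache counts and the early/late rates are illustrations, not predictions. The conclusion rests on the table titles in SAP 9.2 and the text of SAP 7.4.1; table shells and the CRF are not in the documents.

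The conflict over the reporting period bears directly on the remedy. While 24 weeks stands beside 2 years and 24 months, a low count late in follow-up could mean little harm or little collection.

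**What to change.** 1. Reconcile the AE reporting period first across protocol 16.2, protocol 18.4 and SAP 7.4.1.
2. In protocol 18.4 and SAP 7.4.1, present Tables 14.3.1.1 (all treatment-emergent AEs), 14.3.1.3 (by relationship) and 14.3.1.5 (SAEs) by a small number of prespecified onset windows at existing visits, for example Day 1–8, Day 9–Month 6 and after Month 6–24. Count a patient in each window in which an event of that term begins, use patients under observation at the start of the window as the denominator, and keep the overall column.
3. Add onset study day to the AE, DLT and SAE listings (16.2.18.1, 16.2.18.2 and 16.2.20).
4. State in SAP 7.5 whether AEs after a patient's Month 6 visit enter the interim tables.

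**Cost.** SAP and protocol wording, plus programming. Three windows for three cohorts and the pooled group add 3 × 4 = 12 columns to each table. No new visits are needed, since the schedule already assesses AEs at these times; the fix assumes that the CRF records an onset date. The drawback is sparse cells: an empty late cell in a cohort of 6 still allows a rate up to 39.3%, so the pooled columns will carry most of the information.
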